1.2 Purpose

The study is designed, in conjunction with a second study of identical design conducted in parallel, to provide efficacy, safety and tolerability data for ofatumumab sc compared to oral (po) teriflunomide (Aubagio®) in patients with relapsing MS. The data will support regulatory approval to make ofatumumab sc available for clinical use worldwide as a treatment for this patient population.

2 Study objectives and endpoints

2.1 Primary objective(s)

Demonstrate that ofatumumab 20 mg sc once every 4 (q4) weeks is superior to teriflunomide 14 mg po once daily in reducing the frequency of confirmed relapses as evaluated by the annualized relapse rate (ARR) in patients with relapsing MS.

2.2 Secondary objective(s)

Key secondary objectives

All disability-related key-secondary objectives will be addressed in the combined data (meta-analysis) from this study and the second study of identical design. All other objectives will be addressed based on the data from this study alone.

The key secondary objectives are to evaluate if ofatumumab 20 mg sc q4 weeks is superior to teriflunomide 14 mg po once daily on the following efficacy measures:

- Time to disability worsening as measured by 3-month confirmed worsening (3mCDW) on The Expanded Disability Status Scale (EDSS)
- Time to disability worsening as measured by 6-month confirmed worsening (6mCDW) on EDSS
- Time to disability improvement as measured by 6-month confirmed improvement (6mCDI) on EDSS
- Number of T1 Gd-enhancing lesions per MRI scan
- Number of new or enlarging T2 lesions on MRI per year (annualized T2 lesion rate)
- Neurofilament light chain (NfL) concentration in serum
- Rate of brain volume loss (BVL) based on assessments of percentage brain volume change from baseline

Other secondary objectives

Evaluate if ofatumumab 20 mg sc q4 weeks is superior to teriflunomide 14 mg po once daily on the following efficacy measures:

- Time to first relapse
- Annualized relapse rates > 8 weeks after the onset of treatment
- Risk of a 3mCDW > 8 weeks after the onset of treatment
- Risk of a 6mCDW > 8 weeks after the onset of treatment
- Time to a 6-month confirmed cognitive decline (6mCCD), defined as a 4-point worsening on Symbol Digit Modalities Test (SDMT)
- Time to 6mCDW or 6mCCD, whichever is reached first
- Change in cognitive performance relative to baseline as measured by the SDMT
- Time to 6-month confirmed worsening of at least 20% in the timed 25-foot walk test (T25FW)
- Time to 6-month confirmed worsening of at least 20% in the 9-hole peg test (9HPT)
- Time to 6mCDI sustained until End of Study (EOS) as measured by EDSS
- Number of new or enlarging T2 lesions between Month 12 and EOS
- Change in T2 lesion volume relative to baseline
- Proportion of patients with no evidence of disease activity (NEDA-4; defined in [Section 9.5.1.2](#)) at year 1 and 2
- Physical and psychological impact of MS disease as measured by the Multiple Sclerosis Impact Scale (MSIS-29)

[figure not shown]
In the subgroup of newly diagnosed, treatment-naïve patients, evaluate if:

- High NfL (above median) concentration at baseline is predictive of higher disease activity post baseline
- Patients with a high NfL (above median) concentration at baseline benefit from a stronger relative treatment effect of ofatumumab vs teriflunomide
- The safety profile of ofatumumab vs teriflunomide is comparable in patients with high NfL (above median) concentration at baseline

Evaluate the safety and tolerability of ofatumumab 20 mg sc q4 weeks compared to teriflunomide 14 mg po once daily.

Evaluate the pharmacokinetics (PK) of ofatumumab.

3 Investigational plan

3.1 Study design

This is a randomized, double-blind, double-dummy, active comparator-controlled, parallel-group, multi-center study with variable treatment duration in approximately 900 patients with relapsing MS. The treatment duration for individual patients will be variable based on when the End of Study (EOS) criteria are met. The maximal duration for an individual patient will be 30 months (2.5 years).

Eligible patients will be randomized to receive either ofatumumab 20 mg sc injections q4 weeks (after initial loading regimen of three weekly 20 mg doses in the first 14 days) or teriflunomide 14 mg orally once daily. In order to blind for the different formulations, a double-dummy design will be used: patients in the active ofatumumab treatment arm will additionally take placebo capsules orally once daily; patients in the active teriflunomide treatment arm will additionally take q4 weeks placebo-containing sc injections (after initial regimen of three weekly injections in the first 14 days) ([Section 5.5](#)). Other measures to protect study blind include:

- Use of an *independent EDSS rater* for clinical efficacy assessments ([Section 5.6.6](#)), who is not the same person as the *Investigator* ([Section 5.6.6](#))
- MRI scans are read by a blinded central MRI reading center ([Section 6.4.3](#))
- And laboratory assessments that may lead to potential unblinding ([Section 6.5.4](#)) will not be revealed to the site staff or Sponsor study team.

A second study of identical design (COMB157G2301) will be conducted simultaneously. Both studies have the same primary (reduction in ARR) and key-secondary objectives. Both studies will be conducted globally, but individual sites can only participate in one study to ensure independence between the 2 studies. Key-secondary hypotheses with high sample size requirements, i.e. those related to disability worsening or disability improvement, will be tested on the basis of the combined data from the 2 studies (meta-analysis). Multiplicity adjustments are defined in [Section 9.4.1.1](#). Poolability of the 2 studies will be assumed on the basis of the identical design, the simultaneous and global conduct of the 2 studies. For information only, the heterogeneity of the treatment effect between the 2 studies will be tested for disability-related outcomes in the meta-analysis.

Prior to the completion of enrolment, a blinded data review (i.e. the treatment code will not be broken) will be performed for the 2 studies to re-assess sample size assumptions for ARR (for each study separately) and for 3mCDW (for pooled studies). Based on this blinded review, the number of patients to be enrolled may be increased to a maximum number of 1250 randomized patients in each study ([Section 9.7.2.1](#)).

End of Study (EOS) will be reached for both studies when **all** of the following conditions are met simultaneously:

1. Each study has collected sufficient data to provide 90% power for the primary ARR endpoint.
2. Across the 2 studies, sufficient 3mCDW events have been observed to provide 90% power for the key-secondary 3mCDW endpoint.
3. Across the 2 studies sufficient 6mCDW events have been observed to provide 80% power for the key-secondary 6mCDW endpoint.

An analysis of blinded data will be conducted to determine the time point at which EOS is reached. Blinded data reviews are described in [Section 9.7.2](#) and a formal definition of the EOS criteria can be found in the statistical [Section 9.7.2.2](#).

The EOS analysis will be based on the completed core study i.e. based on all patients who have completed the Treatment epoch including partial data from the Safety Follow-up epoch available at the time of EOS cut-off ([Section 9.5.2.6](#)).

The core study consists of 3 epochs; **Screening epoch** (including Baseline), **Treatment epoch** (double-blind) and **Safety Follow-up (FU) epoch** ([Figure 3-1](#)). Patients who complete the double-blind Treatment epoch may be eligible to enter an open-label ofatumumab Extension study that is planned (under separate protocol). Patients who complete the Treatment epoch (on study drug), but do not enter the Extension study will be followed up for safety in the Safety Follow-up (Safety FU) for a minimum of 9 months.

The **Screening epoch** can last up to 45 days and consists of 2 periods, Screening and Baseline: The Baseline period can last up to the point of first study drug administration (Day -7 to Day 1). Patient eligibility will be determined based on the Screening and/or Baseline assessments. If a patient is declared a screen failure, he/she may be rescreened and all assessments must be repeated.

The double-blind **Treatment epoch** will start on Day 1 with randomization of the patient. Patients will be randomly assigned to receive either sc ofatumumab or oral teriflunomide in a double-blind, double-dummy fashion. In the first 4 weeks, injectable study treatment (ofatumumab or placebo) will be administered on Day 1, Day 7 and Day 14 and Day 28 (Week 4, study Month 1). Thereafter, injections will be administered every 4 weeks. All patients will also take one capsule orally once daily (teriflunomide or placebo) starting on Day 1. The Treatment epoch for an individual patient will continue until the End of Study (EOS) has been declared, or for a maximal duration of 30 months, if the EOS has not been declared earlier.

All patients will receive their first sc injection at the site administered by the study staff (Investigator or Study Nurse/Study Coordinator), and will return to the site on Day 7, Day 14 and Day 28 (Month 1) for sc injections under supervision of the study staff (refer to [Section](#)

5.5.4 for further details). Patients will thereafter return to the site for assessments at Month 3 and every 3 months thereafter for the duration of the Treatment epoch. All patients will have an EOS Visit at the end of the Treatment epoch (either when EOS is declared for all patients, or when the patient has reached the maximum of 30 months, or if the patient discontinues from study drug and is not willing to follow the Treatment epoch visits and assessments further).

Patients who prematurely discontinue double-blind study medication and agree to continue to follow the assessment schedule of the Treatment epoch (recommended) will have their end of treatment (EOT) visit and assessments at the time of study medication discontinuation. These patients will then be asked to continue to follow the schedule of assessments (Table 6-1) and have their EOS Visit at the end of the Treatment epoch. After study drug discontinuation, patients may initiate alternative MS therapy according to local standard of care if clinically indicated (see Section 5.6.2).

The **Safety FU epoch** (Table 6-2) will be applicable for the following patients:

- Patients who complete the Treatment epoch on study drug and do not enter the planned Extension study
- Patients who prematurely discontinue study treatment and do not agree to continue to be followed in the Treatment epoch
- Patients who have prematurely discontinued study treatment, are being followed in the Treatment epoch but have had less than 9 months of off-treatment follow up at the time of EOS/Month 30 (whichever is earlier)

All Safety FU visits must be scheduled relative to the EOS Visit.

All patients will be followed for a total of at least 9 months after study drug discontinuation in the Treatment epoch and/or the Safety FU epoch (by 9 months the vast majority of patients are expected to have repleted their circulating B-cells, see Section 3.3). The duration of the Safety FU epoch for an individual patient will depend on how long the patient has been off study drug at the time he/she enters the Safety FU epoch. For example, a patient who completes the Treatment epoch on study drug and has EOS (and does not enter the extension study), will be followed for at least 9 months in the Safety FU epoch. However, a patient who discontinues study drug at an earlier time point and had 4 months of follow up after study drug discontinuation in the Treatment epoch, may only need to be followed for an additional 5 months in the Safety FU epoch (for a total of 9 months).

A longer than 9 months of post-treatment follow up in the Safety FU epoch will be required for the following patients:

- Patients who have not repleted their B-cells (i.e. B-cells not back to baseline value or to lower limit of normal (LLN) whichever comes first as determined by central lab) at 9 months
- Patients in whom teriflunomide plasma levels are above 0.02 mg/L (analyzed centrally) at 9 months

[figure not shown]
These patients will continue to be followed with 3-monthly assessments until their B-cell counts have repleted or teriflunomide plasma levels are below 0.02 mg/L. To protect the study blind, the assessment of B-cell counts and teriflunomide plasma levels will be performed centrally and the Investigators and Sponsor study team will only be informed of whether or not continued follow up is necessary.

Patients who have initiated therapy with another disease modifying/immunosuppressive therapy before the end of the 9-month follow up will not be monitored beyond 9 months.

Due to the long elimination of teriflunomide (8 months up to 2 years), all patients who have discontinued study drug and have completed at least 9 months of follow up (in the Treatment epoch or the Safety FU epoch) and who plan to become pregnant/father a child or do not agree to continue to use highly effective contraception, should undergo the teriflunomide-accelerated elimination procedure (AEP) described in Section 7.8. To protect study blind, the decision to do the accelerated elimination procedure must be made without knowledge of the core study treatment assignment. Patients may not re-start study drug after accelerated elimination.

Patients who complete the Treatment epoch (while on study drug) may be eligible to participate in the long-term, open-label ofatumumab **Extension study**. The details of the design and assessments of the Extension study will be described in a separate protocol. This extension will last for up to 5 years for individual patients or until the development of ofatumumab in relapsing MS has been decided to be discontinued, if earlier.

Figure 3-1 Study design

*Patients who complete the Treatment Epoch and do not enter the planned Extension study or who prematurely discontinue study drug and do not agree to complete the study Treatment epoch or have less than 9 months of follow up after study drug discontinuation, will enter the Safety FU epoch. **Extension study will be conducted under separate protocol. M=month, EOS=End of Study, FU=Follow-Up, po qd= orally once a day

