4.2 Exclusion criteria

Patients fulfilling **any** of the following criteria are not eligible for inclusion in this study. No additional exclusions may be applied by the Investigator, in order to ensure that the study population will be representative of all eligible patients.

1. Patients suspected of not being able or willing to cooperate or comply with study protocol requirements in the opinion of the Investigator
2. Patients with primary progressive MS ([Polman et al. 2011](#)) or SPMS without disease activity ([Lublin et al. 2014](#))
3. Patients meeting criteria for neuromyelitis optica ([Wingerchuk et al. 2006](#))
4. Disease duration of more than 10 years in patients with EDSS score of 2 or less
5. Pregnant or nursing (lactating) women, where pregnancy is defined as the state of a female after conception and until the termination of gestation, confirmed by a positive hCG laboratory test.
6. Women of child-bearing potential, defined as all women physiologically capable of becoming pregnant, unless they are using highly effective methods of contraception during dosing and for at least 12 months after stopping study medication. Given the long elimination time of teriflunomide of up to 2 years, women planning to become pregnant may undergo the accelerated elimination process (as per teriflunomide label) after the 12-month period. Highly effective contraception methods include:
 - Total abstinence (when this is in line with the preferred and usual lifestyle of the subject, if accepted by the local regulation). Periodic abstinence (e.g., calendar, ovulation, symptothermal, post-ovulation methods) and withdrawal are not acceptable methods of contraception.
 - Female sterilization (have had surgical bilateral oophorectomy with or without hysterectomy), total hysterectomy or tubal ligation at least six weeks before taking investigational drug. In case of oophorectomy alone, only when the reproductive status of the woman has been confirmed by follow up hormone level assessment
 - Male partner sterilization (at least 6 months prior to Screening). For female patients on the study, the vasectomized male partner should be the sole partner.

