5.6 Study Completion and Discontinuation

5.6.1 Study completion and post-study treatment

A patient has completed the core study when the patient has completed the End of Study (EOS) visit of the double-blind core study Treatment epoch.

The core study is completed for all patients when EOS is declared for the study as described in [Section 3.1](#).

Patients, who complete the core study ([Table 6-1](#)) on study drug, may be eligible for inclusion in the planned Extension study (under separate protocol).

Patients who complete the core study on study drug and do not enter the Extension study will enter the Safety Follow-up period ([Table 6-2](#)) for continued follow up.

Patients who prematurely discontinue study drug and either a) complete the core study Treatment epoch off study drug but have less than 9 months of follow up after study drug discontinuation, or b) do not agree to complete the Treatment epoch, will enter the Safety Follow-up period ([Table 6-2](#)) for continued follow up.

The Safety Follow-up is complete when all patients who entered have been followed for the stipulated period of time or have withdrawn participation prematurely.

The Investigator must provide follow-up medical care for all patients who are prematurely withdrawn from the study, or must refer them for appropriate ongoing care.

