Table 6-1 Assessment schedule

Epoch	Screening		Treatment											
Visit	SCR (D-45 to D-8)	BL (D -7 to D1 (pre- treat ment)	D1 ¹	D7	D14	M1	M3	M6	M9	M12/24	M15/21/27 ⁹	M18	EOT ⁹	EOS ⁹
Visit No.	1	2	101	102	103	104	105	106	107	108/112	109/111/113	110	198	199
Visit Window (days)	n.a.	n.a.	n.a.	±1	±1	±3	±14	±14	±14	±14	±14	±14	n.a.	n.a.
Informed consent	X													
Demography, Height	X													
Medical history	X													
MS History/Treatments	X													
Incl/Excl	X ¹⁸	X												
IRT contact	X		X	X	X	X	X	X	X	X	X	X	X	X
Dispense study drug			X	X	X	X	X	X	X	X	X	X		
Phone interview						monthly between scheduled visits ¹¹								
Physical Exam ²¹	X ^{2a}	X ^{2a}						X		X		X	X	X
Patient diary review							X	X	X	X	X	X	X	X
Contraception status ¹⁶	X	X				X	X	X	X	X	X	X	X	X
Vital signs, Weight	X	X	X ²⁰	X ²⁰	X ²⁰	X ²⁰	X	X	X	X	X	X	X	X
Routine lab samples ¹⁹ , including urine	X ³	X ²³				X	X	X	X	X	X	X	X	X
Sample for B-cells	X	X		X	X	X	X	X	X	X	X	X	X	X
Teriflunomide plasma levels														X ¹⁵
Additional LFT testing					X ¹⁰	X ¹⁰								
Sample for Total IgG, IgM	X ^{2a}	X ^{2a}				X	X	X	X	X	X	X	X	X

Epoch	Screening		Treatment												
Visit	SCR (D-45 to D-8)	BL (D -7 to D1 (pre- treat ment))	D1 ¹	D7	D14	M1	M3	M6	M9	M12/24	M15/21/27 ⁹	M18	EOT ⁹	EOS ⁹	
Visit No.	1	2	101	102	103	104	105	106	107	108/112	109/111/113	110	198	199	
Pregnancy Test ⁴	X		X			X	X	X	X	X	X	X	X	X	
ECG	X ^{2a}	X ^{2a}											X	X	
MRI	X									X			X ⁸	X ⁸	
AEs	X	X	X	X	X	X	X	X	X	X	X	X	X	X	
Prior/Con Meds ¹⁴	X	X	X	X	X	X	X	X	X	X	X	X	X	X	
Sample for population PK ¹³		X				X	X	X		X			X	X	
Sample for ADA ¹³		X				X		X		X			X	X	
Samples for biomarkers ²²	X ^{2a}	X ^{2a}					X			X			X	X	
eCSSRS	X ⁶	X ⁶	X	X	X	X	X	X	X	X	X	X	X	X	
MS Relapse			X	X	X	X	X	X	X	X	X	X	X	X	
EDSS	X	X ^{2b}	X ^{2b}				X	X	X	X	X	X	X	X	
T25FW	X ^{2a}	X ^{2a}					X	X	X	X	X	X	X	X	
9HPT	X ^{2a}	X ^{2a}						X		X		X	X	X	
SDMT (oral)	X ^{2a}	X ^{2a}						X		X		X	X	X	
MSIS-29 ⁷	X ^{2a}	X ^{2a}						X		X		X	X	X	
PRO completion form	X ^{2a}	X ^{2a}						X		X		X	X	X	
AEP			X ¹²												
End of Treatment														X	X ¹⁷

Epoch	Screening		Treatment											
Visit	SCR (D-45 to D-8)	BL (D -7 to D1 (pre- treat ment))	D1 ¹	D7	D14	M1	M3	M6	M9	M12/24	M15/21/27 ⁹	M18	EOT ⁹	EOS ⁹
Visit No.	1	2	101	102	103	104	105	106	107	108/112	109/111/113	110	198	199
Study Phase Completion														X

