10. Additional monthly LFT testing will be required at Month 2, 4 and 5 i.e. between scheduled lab visits in first 6 months in all patients. More frequent LFT testing may be required in patients in countries/regions where the local teriflunomide prescribing information stipulates more frequent LFT testing. E.g. in the EU LFT testing should be performed every 2 weeks in the first 6 months and every 8 weeks thereafter (i.e., once between 3-monthly scheduled visits). A local lab for the additional LFT testing may be used ([Section 6.5.4.2](#))
 11. Telephone interview by site staff every month starting at Month 2. The interview should take place around time of the monthly sc self/home injection to query about any new or worsening symptoms warranting an unscheduled visit, injection reactions, results of home pregnancy testing, compliance with contraception requirements and compliance with local LFT lab testing as applicable
 12. AEP: applicable only for patients who have permanently discontinued study drug. Patients may undergo an accelerated elimination process at Investigator's discretion ([Section 7.8](#))
 13. PK and ADA visits: at the Month 1 visit, the PK and ADA samples should be drawn before the patient takes their Month 1 injection. For later PK and ADA visits, if the monthly injection is scheduled for the same day as the visit, the patient should take the injection after the PK/ADA sample has been drawn (patient should be instructed not to take the injection before coming to the site for the visit)
 14. Including corticosteroids used to treat MS relapse; any newly started MS treatment as applicable (for patients who have discontinued study medications)
 15. Only for patients who had EOT \geq 9 months earlier
 16. Patients contraception status must be reviewed and documented to ensure method of contraception continues to be appropriate per protocol requirement for highly effective contraception
 17. Only for patients for whom the EOT page has not already been completed (i.e. have not had an EOT visit)
 18. Syphilis and Tuberculosis testing must be done as part of eligibility check (Exclusion criterion #11) unless completed in the last 6 months prior to screening with documented negative results. If sites don't have the possibility to test tuberculosis locally, Quantiferon®-TB Gold test may be requested to be done by the Central laboratory to assess patient's eligibility.

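### For patients at least 9 months off drug at End of Study, the Safety Follow-up entry lists contradict the rule for prolonged follow-up, and the 9-month teriflunomide level is scheduled only at End of Study

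*Protocol*

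**What the plan says.** **Who must be followed longer.** Protocol Section 3.1 states: "A longer than 9 months of post-treatment follow up in the Safety FU epoch will be required for the following patients". Two groups are listed: patients whose B-cells have not repleted at 9 months, and "Patients in whom teriflunomide plasma levels are above 0.02 mg/L (analyzed centrally) at 9 months". They are to be assessed every 3 months until repleted or cleared. Protocol Section 3.2 and SAP Section 1.1 agree. Patients who start another disease-modifying or immunosuppressive therapy within the 9 months are exempt.

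**Who enters Safety FU.** Among patients who stopped drug early, the Section 3.1 entry list takes those who decline Treatment-epoch follow-up, and those who "are being followed in the Treatment epoch but have had less than 9 months of off-treatment follow up" at EOS or Month 30. Section 5.6.1 has the same limit: patients who "complete the core study Treatment epoch off study drug but have less than 9 months of follow up after study drug discontinuation". The note at the end of Section 5.6.2 repeats it. The Figure 3-1 footnote (also in the SAP) is broader. Its first clause covers Treatment-epoch completers who do not go into the Extension, with no on-drug condition and no 9-month limit.

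**When the level is drawn.** In Table 6-1 the row "Teriflunomide plasma levels" has one mark, in the EOS column, with footnote 15: "Only for patients who had EOT" at least 9 months earlier. Table 6-2 footnote 6 instead draws the level once total follow-up reaches 9 months, then 3-monthly as needed.

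**Accelerated elimination.** Section 3.1 says it should be done after at least 9 months of follow-up in patients "who plan to become pregnant/father a child or do not agree to continue to use highly effective contraception". Exclusion criterion 6 says "women planning to become pregnant may undergo the accelerated elimination process (as per teriflunomide label) after the 12-month period". Section 7.8 and Table 6-1 footnote 12 leave it to the Investigator after permanent discontinuation, with no minimum interval.

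**The concern.** Staying in the Treatment epoch after stopping drug is the path the protocol recommends. A patient on that path who reaches EOS with at least 9 months off drug is the only kind of patient sampled under footnote 15, and is also the kind the less-than-9-months limit leaves out of Safety FU. If the level is above threshold, or B-cells have not repleted, one paragraph of Section 3.1 requires Safety FU. The entry list a few lines earlier, Section 5.6.1 and the Section 5.6.2 note give no entry to it.

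The timing does not fit either. The rule speaks of a level at 9 months, but for these patients no level is scheduled until EOS, whenever that falls.

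What is at stake is the safety follow-up of patients who may have taken a comparator for which Section 3.6 lists teratogenicity as a risk and which, by Section 7.8, can take as long as 2 years to clear. A site that applied Section 5.6.1 literally would close out a patient whom Section 3.1 says must still be followed. The efficacy analyses are not affected.

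**Working it through.** **Inputs from the protocol:** 9-month minimum off-drug follow-up and 0.02 mg/L threshold (Section 3.1); 30-month maximum Treatment epoch (Section 3.1); average 8 months and at most 2 years to fall below threshold (Section 7.8). **Assumptions:** the month of stopping, EOS at Month 18 or 24 as alternatives to the 30-month maximum, and the End of Treatment visit taken to coincide with stopping.

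**The plan's own example.** Remaining Safety FU = max(0, 9 − months off drug at EOS). With 4 months off drug, 9 − 4 = 5 months, as Section 3.1 states.

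**Applying the entry rule.** With 9 or more months off drug at EOS, the same formula gives 0 months due, and the entry lists do not admit the patient. Footnote 15 selects exactly this group for sampling. On these passages, the patients sampled at EOS and the off-drug completers admitted to Safety FU do not overlap.

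**Delay of the only Treatment-epoch draw.** Delay past the 9-month point = (EOS month − stop month) − 9.

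| Stop month | EOS Month 18 | EOS Month 24 | EOS Month 30 |
|---|---|---|---|
| 1 | 8 | 14 | 20 |
| 6 | 3 | 9 | 15 |
| 12 | under 9 months off drug | 3 | 9 |
| 18 | – | under 9 months off drug | 3 |

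For example, 30 − 1 = 29 months off drug and 29 − 9 = 20 months' delay. The delay is 0 when drug stops exactly 9 months before EOS (Months 9, 15 and 21 respectively).

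**Where a positive result is plausible.** If clearance takes at most 24 months, an above-threshold level is to be expected mainly between 9 and 24 months off drug. Within that range the delay is at most 24 − 9 = 15 months.

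**Comparison path.** Patients with 0 to 8 months off drug at EOS are on the entry lists. With Safety FU visits at +3, +6 and +9 months, their first draw under Table 6-2 footnote 6 falls at 9 to 11 months in total (for example 3 + 6 = 9, 4 + 6 = 10, 5 + 6 = 11). The mismatch is therefore confined to patients with at least 9 months off drug at EOS.

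**B-cells.** Table 6-1 marks B-cell samples at every scheduled visit from Day 7, so the timing gap concerns teriflunomide only. The entry contradiction covers both criteria.

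**The case against.** The case for leaving the text alone has four parts.

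- **The 9-month test decides only whether follow-up continues.** A patient off drug in the Treatment epoch is seen every 3 months until EOS anyway, so the decision first takes effect at EOS, when the sample is drawn. This largely stands. The delay is not a period without follow-up. The literal mismatch remains, as does the difference from Table 6-2.
- **Continued follow-up is provided for.** Sections 3.1 and 3.2 and SAP Section 1.1 require it, Table 6-2 has an every-3-months column for it, the Figure 3-1 footnote can be read to admit these patients, and the Investigator is told centrally whether more follow-up is needed. This stands against any inference that an above-threshold result at EOS leads nowhere. It does not remove the conflict with the entry passages.
- **Elimination does not wait for the level.** It must be decided without knowledge of treatment assignment and is available after discontinuation at the Investigator's discretion. A minimum of 9 months also does not exclude 12. Both points are correct, but the three statements still differ on when it applies.
- **The group is narrow.** Patients who start another therapy within the 9 months are exempt, and for the teriflunomide level only one arm matters. This stands.

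A reader might also infer that repletion data are lost. The documents do not show this before EOS: B-cells are scheduled throughout, and SAP Sections 2.1.2.2 and 2.8.7 summarise post-discontinuation counts from both epochs. The grey shading that marks off-drug assessments in Table 6-1 cannot be seen in the text available, and nothing is held against the plan on that account.

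**Conclusion.** The protocol contradicts itself for one group: patients who stop drug early, stay in the Treatment epoch and are at least 9 months off drug at EOS. The prolonged-follow-up rule requires Safety FU if they are not cleared or repleted. Two entry lists and one note leave them out, and a figure footnote can be read to let them in. Separately, the level described as taken at 9 months is scheduled for them only at EOS, up to 20 months later at the extreme and up to 15 months later within the 2-year clearance range. These figures rest on assumed stopping and EOS months within the 30-month maximum. The timing of accelerated elimination is inconsistent across Section 3.1, criterion 6, and Section 7.8 with footnote 12.

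A reader might go further and estimate how many patients are affected. The documents give no rate of stopping drug while staying in the study, and the 20% dropout allowance in the sample-size section is not that rate, so no count is offered. The effect on reported results is small, because SAP Section 2.8.7 only lists teriflunomide levels. The point is worth correcting because it bears on safety follow-up and the correction is cheap.

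**What to change.** Amend the protocol so that the passages agree:

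1. Reconcile the Safety FU entry lists in Sections 3.1 and 5.6.1, the Section 5.6.2 note and the Figure 3-1 footnote with the Section 3.1 list of patients needing more than 9 months, so that all name the same patients. Carry any change into SAP Section 1.1 and its Figure 1-1 footnote.
2. Reconcile the 9-month wording in Section 3.1 with the Table 6-1 sampling point and footnote 15, and state how it relates to Table 6-2 footnote 6.
3. Reconcile the accelerated-elimination timing in Section 3.1, exclusion criterion 6, Table 6-1 footnote 12 and Section 7.8.

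Which follow-up, sampling and elimination rule applies is a clinical decision for the sponsor, and none is proposed here. The cost is amendment wording and, depending on that decision, possibly one central assay at an existing 3-monthly visit. Any Safety FU visits that follow are ones Section 3.1 already requires.
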